# 2.5.1 **Primary endpoint**

The primary endpoint is the proportion of patients experiencing histological response, which is defined as resolution of NASH (absence of ballooning with no or minimal inflammation by histology) and no worsening of fibrosis OR improvement in fibrosis by at least one stage without worsening of NASH (worsening of hepatocellular ballooning or lobular inflammation) at week 48 compared with baseline. The criteria for resolution of NASH (absence of ballooning with no or minimal inflammation by histology) and other changes in histologic endpoints are further detailed in Section 5.3.11.

# 2.5.2 Statistical hypothesis, model, and method of analysis

To demonstrate improved efficacy of tropifexor+licogliflozin in combination, the response rate in the combination arm will be compared with each monotherapy arm. A one-sided test ( $\propto$ =0.05) of statistical superiority is planned for each comparison. A stepwise gatekeeping hierarchical test procedure, in which the second test is only performed if the first null hypothesis is rejected, will be adopted to maximize the power for the first test while still maintaining a strong control of family wise type 1 error rate (FWER-1) at 0.05.

The hierarchical testing will be performed in the following sequence.

- 1. Combination vs. licogliflozin (LIK066)
- 2. Combination vs. tropifexor (LJN452)

The order of the hierarchical tests is determined under a preliminary assumption that tropifexor, by targeting the Farnesoid X receptor that directly modulates liver inflammation and fibrosis associated with NASH, could potentially be more effective than licogliflozin hence results in smaller add-on effect of the combination when used as the reference in the comparison. If external data newly available during the study warrants different assumptions, the order of tests could be switched before the study unblinding without inflation of the FWER-1.

For these two tests on the same endpoint and sharing a common comparator (combination arm), the hierarchical testing approach also allows an intrinsic adjustment of the correlation between them for the power of the second test.

The proportions of histological responders in the three treatment arms are assumed following binomial distributions (**n**, **P**) and the sample distribution of the difference  $p_1-p_{2i}$  will be asymptotically normal with mean P1-P2i and variance P1\*(1-P1)/n1 + P2i\*(1-P2i)/n2i., where

 $i \in \{1, 2\}$  ~ the level of the hierarchical test

 $\mathbf{P} = (P_1, P_{21}, P_{22}) \sim$  True probabilities of histological responses after 48 weeks of treatment with the combination, licogliflozin and tropifexor respectively

Novartis	For business use only	Page 21
SAP		CLJN452D12201C

 $\mathbf{n} = (n_1, n_{21}, n_{22}) \sim \text{Number of patients in the combination, licogliflozin and tropifexor groups respectively in the study}$ 

 $\mathbf{p} = (p_1, p_{21}, p_{22}) \sim$  Proportion of histological responders observed in the study after 48 weeks of treatment with the combination, licogliflozin and tropifexor respectively

With the sample data collected in the study, the naive differences  $P_1-P_{2i}$  can be estimated using  $p_1-p_{2i}$  with unpooled standard error SE = sqrt(  $p_1*(1-p_1)/n_1 + p_{2i}*(1-p_{2i})/n_{2i}$ ).

The hierarchical testing procedure based on odds ratio can be formulated as one-sided statistical tests ( $\alpha$ =0.05) for

H0i: 
$$\frac{P1(1-P2_i)}{P2(1-P1_i)} \le 1$$
 vs. H1i:  $\frac{P1(1-P2_i)}{P2(1-P1_i)} \ge 1$ 

executed sequentially for i=(1, 2), where H02 is tested only if H01 is rejected.

A logistic regression model with the logit of probability for histological response as the dependent variable, treatment groups as the main effect, baseline fibrosis stage (2 vs. 3) and T2DM (No/Yes) status as co-factors, and baseline BMI as a covariate will be utilized to test the hypothesis at each step of the hierarchical testing procedure.

The choice of co-factors/covariates, the considerations for their collinearity, potential interactions with treatment effect and model specifications are further discussed in Section 5.4.1.

The logistic regression analyses can be implemented in SAS LOGISTIC procedure with the *scale=williams* and *firth* options in the model statement, executed together with the multiple imputation (MI) methods outlined in Section 2.5.3.

Odds ratios and 95% CI of the probabilities of histologic response between study treatments can be back calculated as the exponentiation of the corresponding coefficients estimated from the logistic regression.

One logistic regression model can be fitted on all FAS data from the three treatment arms to estimate the pairwise odds ratios and associated p-values.

Given placebo effects (Table 3-1) reported in the published literature and with Firth correction, a model convergence issue is not expected. In the case a convergence issue occurs and cannot be resolved with other appropriate technical approaches, a reduced model may be used for the primary analysis. The reduced model will be determined by removing baseline BMI, fibrosis stage and T2DM status sequentially from the full model until the convergence issue is resolved. If a reduced model has to be used, impacts on the interpretation of primary analysis results will be discussed in the core CSR in combination with results from sensitivity analysis.

Existence of extremely influential baseline BMI values will be examined with Cook's distance plot based on complete cases before MI.

The numbers and percentages of histological responders will be summarized by study treatment. The difference between the combination therapy and each monotherapy will be presented along with 95% CI calculated based on the normal approximation for distribution of the difference

Novartis	For business use only	Page 22
SAP		CLJN452D12201C

between two binomial random variables (Wald asymptotic CI). Odds ratios (95% CI) and p-values from the logistic regression model will be reported.

# 2.5.3 Handling of missing values/censoring/discontinuations

Especially due to the clinical burden of liver biopsy, missing data is possible and could be related to observable data or even the unobserved primary endpoint.

While not possible to confirm missing completely at random (MCAR), the histological response status from the early termination visit after at least 24 weeks of study treatment will be used for the primary analysis in case of missing primary endpoint at week 48. Patients otherwise with primary endpoint missing or any primary endpoint after intercurrent events will have the values imputed using multiple imputation (MI) methods (Rubin 1976, 1987) under a missing at random (MAR) assumption.

An arbitrary missing pattern will be assumed and a fully conditional specification (FCS) method with logistic regression will be applied. Baseline fibrosis stage (2 vs. 3), baseline T2DM (No/Yes), baseline BMI (as categorical predictor) and decrease of ALT at week 24 ( $\leq$  -17 U/L vs. >-17 U/L) will be included as predictors for the imputer's model. The logistic model outlined for primary analysis will be used to analyze the multiply imputed datasets, and pooled results will be obtained based on Rubin's combination rules.

More details for the MI method are discussed in Section 5.4.2.

The MI methods may be implemented using the SAS MI procedure with FCS LOGISTIC statement and the MIANALYZE procedure. The order of variable imputation will be specified with ORDER=VAR option in FCS statement. The VAR statement will list variables for baseline fibrosis stage (2 vs. 3), baseline T2DM status (No/Yes), baseline BMI (as continuous predictor) and decrease of ALT at week 24 (<= -17 U/L vs. >-17 U/L) in sequence. The number of imputations will be set to 50.

The number (%) of patients with missing primary endpoint at week 48 will be summarized by study treatment.

#### 2.5.4 Supportive analyses

Supportive analyses will be performed to cross check with the results from primary analysis.

- The primary analysis will be repeated with an intent-to-treat (ITT) approach, recognizing that inter-current events could happen in real clinical practice potentially as a result of the treatment policy. Patients' histological response status collected at week 48 or early termination visit will be used in this sensitivity analysis regardless of inter-current event(s). Patients otherwise with missing primary endpoint will be counted as non-responders. This approach is considered more conservative for estimating the benefit of combination therapy.
- Tests in the two hierarchical steps of primary analysis will be repeated separately
  using Cochran-Mantel-Haenszel (CMH) method stratified by baseline fibrosis stage (2
  vs. 3), T2DM (No/Yes) and BMI (>= 35 vs. < 35). Primary endpoint observed at week
  48 or last visit after at least 24 weeks of exposure to study treatment will be used
  regardless of intercurrent event(s). Patients otherwise will be counted as non-

Novartis	For business use only	Page 23
SAP		CLJN452D12201C

responders. More details on the CMH methods are discussed in Section 5.4.4. The CMH analysis may be implemented using SAS FREQ procedure with the CMH option in TABLES statement.

# 2.6 Analysis of the key secondary objective

Descriptive summaries of key secondary endpoints (Table 2-4) will be presented by study treatment on FAS. Hypothesis tests for treatment differences in key secondary endpoints will be performed if and only if both null hypothesis in the primary analysis are rejected.

# 2.6.1 Key secondary endpoints

Table 2-4	Key secondary endpoints and methods of analysis
-----------	---

Endpoints	Analysis method
Key secondary endpoint: Proportion of patients achieving at least one point improvement of fibrosis stage without worsening of NASH (no worsening of hepatocellular ballooning or lobular inflammation) at Week 48 compared with baseline	Same logistic regression model as used in the primary analysis for each step of hierarchical test
Key secondary endpoint: Proportion of patients achieving resolution of NASH without worsening of fibrosis stage at Week 48 compared with baseline	Same logistic regression model as used in the primary analysis for each step of hierarchical test

#### 2.6.2 Statistical hypothesis, model, and method of analysis

Extending the hierarchical testing procedure for primary analysis and defining a general onesided ( $\alpha$ =0.05) statistical hypothesis test H*i* for

$$Hi_0: \frac{Pi_1(1-Pi_2)}{Pi_2(1-Pi_1)} <= 1 \text{ vs. } Hi_1: \frac{Pi_1(1-Pi_2)}{Pi_2(1-Pi_1)} > 1$$

at each step of hypothesis test, where i=1, ..., 6 with  $Pi_1$  and  $Pi_2$  correspond to the true probabilities of response for combination vs. monotherapy in the *i*th test, the extended hierarchical testing procedure can be formalized following general principles in the graphical approach (Bretz et al 2009) to maintain a strong control of an overall type I FWER at 0.05. where

- H1: Combo vs. LIK066 comparison in primary endpoint (Section 2.5.2)
- H2: Combo vs. LJN452 comparison in primary endpoint (Section 2.5.2)
- H3: Combo vs. LIK066 comparison in proportion of patients achieving at least one point improvement of fibrosis stage without worsening of NASH (no worsening of hepatocellular ballooning or lobular inflammation) at Week 48 compared with baseline
- H4: Combo vs. LJN452 comparison in proportion of patients achieving at least one point improvement of fibrosis stage without worsening of NASH (no worsening of hepatocellular ballooning or lobular inflammation) at Week 48 compared with baseline
- H5: Combo vs. LIK066 comparison in proportion of patients achieving resolution of NASH without worsening of fibrosis stage at Week 48 compared with baseline

H6: Combo vs. LJN452 comparison in proportion of patients achieving resolution of NASH without worsening of fibrosis stage at Week 48 compared with baseline

A specific hypothesis test H*i* will be performed if and only if the null hypotheses in all previous testing steps are rejected.

The number (%) of responders will be summarized by study treatment. The difference between the combination therapy and each monotherapy will be presented along with Wald asymptotic 95% CI. The same logistic regression model and MI method for primary analysis will be adopted for hypothesis tests on key secondary endpoints and odds ratios (95% CI) will be presented. If no hypothesis test is performed for a step based on the pre-specified hierarchical testing procedure, the p-values will not be reported.

# 2.6.3 Handling of missing values/censoring/discontinuations

The same MI methods outlined in Section 2.5.3 for primary analysis will be used for missing data imputation during key secondary analysis.

# 2.7 Analysis of secondary efficacy objective(s)

Secondary efficacy endpoints in Table 2-5 will be summarized by visit and by study treatment on FAS.

#### 2.7.1 Secondary efficacy endpoints

Endpoint	Analysis
Proportion of patients who have at least one stage improvement in fibrosis at week 48 compared with baseline	Same analysis methods as for the primary endpoint following the ITT principle (Section 2.5.4 ) without hypothesis test.
Proportion of patients who have at least two stage improvement in fibrosis and no worsening of NASH (no worsening of hepatocellular ballooning or lobular inflammation) at week 48 compared with baseline	Same analysis methods as for the primary endpoint following the ITT principle (Section 2.5.4 ) without hypothesis test.
Change in liver fat content based on MRI - PDFF (in 60% of patients) over time up to Week 48 compared with baseline	Repeated measurement analysis of covariance (ANCOVA) model (Section 5.4.3) will be used to estimate treatment group differences in mean change from baseline and 95% CI. This analysis is on FAS patients with at least one MRI-PDFF assessment.
Proportion of patients with 5% or more reduction in body weight at Week 48 compared to baseline	CMH test stratified with baseline T2DM status will be performed to estimate odds ratio (95% CI) between combination arm and each monotherapy

 Table 2-5
 Secondary efficacy variables and methods of analysis

# 2.7.2 Statistical hypothesis, model, and method of analysis

There is no hypothesis test planned for these additional secondary endpoints.

Binary histologic endpoints will be analyzed using the same logistic regression model for primary endpoint following an ITT approach (Section 2.5.4). The number (%) of responders will be summarized by study treatment. The difference between the combination therapy and each monotherapy will be presented along with Wald asymptotic 95% CI. The Odds Ratios (with 95% CI) between combination and each monotherapy estimated from the logistic regression model will also be provided.

Repeated measurements ANCOVA models for the change in liver fat fraction will include time (visit) and treatment group as categorical explanatory variables, with interaction between treatment and visit also included in the model. More details of the model are discussed in Section 5.4.3. The analysis may be implemented with SAS MIXED procedure, assuming an unstructured variance-covariance matrix for repeated measurements and using Kenward-Rogers type degrees of freedom. Estimates of the differences (95% CI) between treatment groups may be obtained using the LSMEANS and ESTIMATE statements in the SAS procedure at individual time points. Descriptive statistics, adjusted mean and adjusted mean differences (95% CI) between combination and monotherapies will be presented by visit.

For proportion of patients with at least 5% reduction of body weight at week 48, the number (%) of patients will be summarized by study treatment. Difference in percentages will be presented with Wald asymptotic 95% CI. A CMH analysis stratified by baseline T2DM status will be performed to estimate the common odds ratio (95% CI) between combination and each monotherapy. CMH analysis may be implemented with the SAS FREQ procedure following similar implementation in the sensitivity analysis on primary endpoint (Section 5.4.4) but with only baseline T2DM status as stratification factor.

# 2.7.3 Handling of missing values/censoring/discontinuations

The repeated measures ANCOVA (MMRM) model implicitly imputes missing data under MAR assumption. For variables with only one post-baseline assessment, a missing post-baseline value will be imputed by the baseline value. Patients without any post-baseline assessment will not be included in the analysis.

Histologic endpoint at the week 48 or early termination visit after at least 24 weeks of exposure to study treatment will be used for secondary efficacy analysis regardless of intercurrent event(s). Patients will otherwise be counted as non-responders.

Missing body weight at week 48 will be imputed by the last non-missing assessment, including baseline value, before week 48 (LOCF).

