12.4.3 Handling of remaining intercurrent events of primary estimand

Intercurrent events of primary estimand will be addressed with various strategies (given that these events occur before the histological assessments at Week 48):

- 1. Bariatric surgery: participants who have undergone bariatric surgeries during trial participation are considered as non-responders (composite variable strategy).
- 2. Use of alcohol above protocol permitted amount: the intercurrent events (overuse of alcohol) will be ignored for estimation (treatment policy strategy).
- 3. Addition or removal of any medication that may have a confounding effect on the endpoints: the treatment effect will be assessed with the intercurrent event ignored (treatment policy strategy). The treatment policy strategy may not be ideal if the confounding medications highly affect the endpoints. Consequently, a supplementary analysis will be conducted where the treatment effect is imputed as if the intercurrent event doesn't occur (hypothetical strategy)
- 4. Premature discontinuation of study treatment due to tolerability, efficacy, adherence, or adverse event: participants who discontinue the treatment after Week 24 will be asked to have their biopsies assessed at Week 48 regardless of the intercurrent event (treatment policy strategy), participants who discontinue the treatment before Week 24 will be considered as non-responders (composite variable strategy), and participants who have no biopsy extracted at Week 48 will be considered as non-responders (composite variable strategy).
- 5. Death, transplantation and other clinical outcomes: participants will be considered as non-responder (composite endpoint strategy).
- 6. Acute medical condition not related to the study treatment affecting the liver: participants will have their Week 48 biopsies assessed regardless of the intercurrent events (treatment policy strategy).
- 7. Acute medical condition related to the study treatment affecting the liver: participants are considered as non-responder (composite endpoint strategy).

Novartis	Confidential	Page 139 of 160
Amended Protocol Version 02 (Clean)		Protocol No. CLJN452D12201C

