12.5.1 Efficacy

endpoint(s)

Secondary efficacy endpoints will be analyzed in the FAS and planned analyses are outlined in Table 12-1 below:

Novartis ---- Confidential

Table 12-1Planned Analyses	
Endpoints	Analysis
Key secondary endpoint: whether the participant achieves resolution of NASH and no worsening of fibrosis OR Improvement in fibrosis by at least one stage without worsening of NASH at Week 48 compared with baseline.	Same statistical methods as for one branch of the primary analysis with overall Type I error rate controlled at two sided 0.05 level.
Whether (yes or no) the participant has at least one stage improvement in fibrosis at week 48 compared with baseline	Same statistical methods as for the key secondary endpoint analysis with neither hypothesis tests nor p-values.
Whether (yes or no) the participant has at least two stage improvement in fibrosis stage and no worsening of NASH at week 48 compared with baseline	Same statistical methods as for the primary analysis with neither hypothesis tests nor p-values.
Change in liver fat content based on MRI - PDFF (in 40% of participants) over time up to Week 48 compared with baseline	Descriptive statistics, adjusted mean and mean differences of treatment of interest vs. alternative treatment with 95% CI by scheduled visits based on repeated measurement analysis of covariance (ANCOVA) model will be presented.
Whether (yes or no) the participant has 5% or more reduction in body weight at Week 48 compared to baseline	Number and percentage of participants with 5% or more reduction in body weight. Difference in percentages between treatment of interest and alternative treatment along with 95% CI calculated based asymptotic normal distribution of difference in proportions will be presented. CMH test stratified with baseline T2DM status will be performed to estimate odds ratio (95% CI) between treatment of interest and alternative treatment.
Change in ALT and AST over time up to Week 48 compared with Baseline	The mixed model of repeated measurement will be fitted to changes from baseline in these endpoints over time. The point estimate and the associated 95% CI of the change from each treatment at each visit will be presented.
Change in GGT over time up to Week 48 compared with Baseline	The mixed model of repeated measurement will be fitted to changes from baseline in GGT over time. The point estimate and the associated 95% CI of the change from each treatment at each visit will be presented.

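### The SAP treats missing biopsies differently for two nested fibrosis endpoints, and carries the last weight forward for the 5% weight-loss endpoint without a rule for bariatric surgery

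*SAP*

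**What the plan says.** **Secondary histology.** SAP Table 2-5 and section 2.7.2 analyse the two secondary fibrosis endpoints (improvement of one stage or more; improvement of two stages or more with NASH not worse) under the ITT approach of section 2.5.4. SAP 2.7.3 says that a biopsy at Week 48, or at early termination after at least 24 weeks of exposure, "will be used for secondary efficacy analysis regardless of intercurrent event(s"; and then: "Patients will otherwise be counted as non-responders".

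**Primary and key secondary histology.** SAP 2.5.3 says: "Patients otherwise with primary endpoint missing or any primary endpoint after intercurrent events will have the values imputed using multiple imputation (MI) methods". SAP 2.6.3 extends this: "The same MI methods outlined in Section 2.5.3 for primary analysis will be used for missing data imputation during key secondary analysis". The key secondary tests include "H3: Combo vs. LIK066 comparison in proportion of patients achieving at least one point improvement of fibrosis stage without worsening of NASH". In protocol version 02 that endpoint is a primary endpoint.

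**Protocol version 02, Table 12-1.** Improvement of one stage or more takes the key secondary method, which is itself the primary method. For improvement of two stages or more the entry reads "Same statistical methods as for the primary analysis with neither hypothesis tests nor p-values".

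**Weight.** SAP 2.7.3 says: "Missing body weight at week 48 will be imputed by the last non-missing assessment, including baseline value, before week 48 (LOCF". For surgery, protocol 12.4.3 says "participants who have undergone bariatric surgeries during trial participation are considered as non-responders", but only within the primary estimand. Neither document gives a rule for surgery in the weight endpoint.

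**The concern.** Call improvement of one fibrosis stage or more the wide endpoint, and the same improvement with NASH not worse the narrow endpoint. Every narrow responder is a wide responder, so the wide rate cannot truly be lower. The SAP fills missing biopsies with imputed responses for the narrow endpoint and with failures for the wide one. The two rates then answer different questions, and their order can reverse. A biopsy taken after an intercurrent event may also be replaced by an imputed value for the narrow endpoint and used as observed for the wide one. A reader comparing the tables to see how much fibrosis improvement comes with worse NASH would be misled.

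For weight, carrying the last value forward treats the last recorded weight as the Week 48 weight. That is a strong assumption for someone who has stopped a drug expected to lower weight. At stake is the credibility of descriptive secondary results, not the success criterion.

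**Working it through.** **Plan's own figure.** SAP Table 3-2 gives 79% power for the first test (70 per arm, 30% vs 50%, one-sided 0.05). The formula gives 78.4% and a simulated z-test without continuity correction 78.7%, so it reproduces. It concerns the SAP's composite primary endpoint, which none of the rules discussed here touch.

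**Reversal of the nested endpoints.** Inputs: narrow rate s = 35% (combination arm, protocol Table 12-3); missing share m = 10% (SAP 3.1, dropout) or 20% (protocol 12.8.1, missing Week 48 biopsies). The extra share x who improve in fibrosis with worse NASH is not given. Missingness is taken as unrelated to response.

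- Narrow endpoint, all missing biopsies imputed: reported rate about s.
- Wide endpoint, missing counted as failure: (s + x)(1 − m).
- The order reverses on average when (s + x)(1 − m) < s, that is x < s·m/(1 − m).
- m = 10%: 0.35 × 0.10/0.90 = 3.9 points.
- m = 20%: 0.35 × 0.20/0.80 = 8.75 points.

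A simulation with 70 per arm and 50 imputations (intercept-only imputation model, a simplification; wide rates assumed) gives:

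| Missing | True narrow / wide | Mean reported narrow / wide | Arms reversed |
|---|---|---|---|
| 10% | 30% / 33% | 30.1% / 29.7% | 57% |
| 10% | 30% / 40% | 30.1% / 36.1% | 6% |
| 10% | 35% / 40% | 35.1% / 36.1% | 38% |
| 20% | 35% / 40% | 35.0% / 32.0% | 81% |
| 20% | 35% / 45% | 34.9% / 35.9% | 41% |

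**Under protocol version 02.** Section 12.4.3 counts discontinuers without a Week 48 biopsy as non-responders, so only a part u of the missing share m is imputed. The narrow rate becomes s(1 − m + u), and the threshold x < s·u/(1 − m). If, say, half of the 20% is imputed (u = 10%, assumed), this is 0.35 × 0.10/0.80 = 4.4 points. It falls to zero as u does.

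**Weight.** Let d be the share with missing Week 48 weight, l the share of these with a loss of at least 5% at the last recorded weight, and t the share who would truly have it at Week 48. The bias in one arm's rate is d(l − t). The documents give no values for l or t, so these are assumed:

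- d = 10%, l = 40%, t = 10%: +3.0 points; with l = 10%, t = 40%: −3.0 points.
- d = 20%, same pairs: +6.0 and −6.0 points.
- Combination minus monotherapy: 0.20(0.40 − 0.10) − 0.10(0.30 − 0.10) = +4.0 points, or 0.10(0.20 − 0.30) − 0.20(0.30 − 0.10) = −5.0 points.

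A second simulation assumed that everyone who leaves drifts back to baseline over 12 to 48 weeks (mean change −4% active, −0.5% placebo; person SD 3.5%, measurement SD 2%). With 20% missing per arm, carrying forward gave an active-placebo difference of 25.4 points against a true 21.9 to 23.5. With 10% missing it gave about 26 against 24.3 to 25.3. The direction follows from the assumed regain.

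**Surgery.** If one post-surgery weight were counted as a response, it would add 1/70 = 1.43 points in an arm of 70, or 1/80 = 1.25 points in an arm of 80.

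**The case against.** The SAP is dated December 2019, describes three arms and 210 patients, and says it may be amended after protocol amendments. Some mismatch with version 02 is therefore expected. That stands as a reason to make the correction in the update, but the split between imputation and non-response lies within the SAP itself.

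Four stronger readings are tempting, and the documents do not support them:

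- **That the wide endpoint can fall below a subset that is the SAP's primary endpoint.** The SAP primary is a composite that NASH resolution alone can satisfy, so it is not a subset of fibrosis improvement. The nested endpoint is a key secondary there and became primary only in the protocol.
- **That the tables will be logically impossible.** The SAP does not say whether the reported numbers of responders use imputed data. Observed counts cannot reverse, and imputation-based rates reverse only when the gap between the endpoints is small.
- **That drug weight loss is overstated.** This needs regain after stopping. A participant who leaves early, before a 5% loss they would have reached, is understated, and one with only a baseline weight becomes a non-responder. Missing weights should also be fewer than missing biopsies: weight is measured at every visit, and the protocol's assessment schedule requires the Week 48 and Week 52 visits after early treatment discontinuation.
- **That the SAP counts surgical weight loss as response.** It is silent. The wording about disregarding intercurrent events is in the histology paragraph only. Prior or planned bariatric surgery is an exclusion criterion, so cases should be few.

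It is also fair to say that non-response is a defensible rule in itself. The difficulty is using it for only one of two nested endpoints.

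**Conclusion.** The concern holds as an inconsistency between nested endpoints and as an unsupported rule for missing weight. With all missing biopsies imputed and a narrow rate of 35%, the imputation-based order reverses on average unless the wide endpoint adds at least 3.9 points at 10% missing or 8.75 points at 20%. This assumes missingness unrelated to response. Under protocol version 02 the thresholds are smaller, by an amount that depends on how many missing biopsies are not tied to intercurrent events.

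For weight, the size and direction of the bias cannot be settled from the documents; the examples run from −6 to +6 points in one arm under assumed inputs. The handling of bariatric surgery is a gap in both documents.

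The SAP plans no hypothesis test on these secondary endpoints, so type I error, stated power and the success criterion are unaffected. The change is worth making because it is specific and cheap.

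**What to change.** When the SAP is updated to protocol version 02:

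1. Derive both secondary fibrosis endpoints with the same intercurrent-event and missing-data rules as the primary endpoints, and from the same imputed biopsies. Impute the biopsy result once per participant and data set and derive every endpoint from it; imputing each endpoint separately could still make someone a narrow responder and a wide non-responder. State whether reported responder counts are observed or imputed.
2. Replace carrying forward for Week 48 weight with multiple imputation from the participant's visit weights, with treatment and discontinuation status in the model. Use non-response for missing weight as a sensitivity analysis.
3. Apply the primary estimand's composite strategy for bariatric surgery (non-responder) to the 5% weight-loss endpoint.

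The cost is SAP wording and programming, and possibly slightly less favourable weight-loss rates. No further data are needed.
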